4.2 Exclusion Criteria

Individuals who meet ANY of the following criteria are not eligible for enrollment:

- 1. Severe or unstable SLE, such as any one of the following:
 - a. A BILAG A score in one or more BILAG domains at Screening
 - b. Treatment with any intraarticular, intravenous, or intramuscular systemic corticosteroids within 14 days of Screening
 - c. Treatment with oral prednisone > 10 mg per day or > 20 mg every other day (or equivalent dose of another corticosteroid) within 14 days of Screening
 - d. Increased dose of systemic corticosteroids in the 14 days prior to Screening
 - e. Treatment with cyclophosphamide or anti-TNFα biologic agents within 3 months before Visit 1 (Day 1)
 - f. Treatment with B cell-depleting monoclonal antibodies (rituximab, Ocrelizumab, anti-CD-22) within 6 months before Visit 1 (Day 1)
 - g. Treatment with methotrexate, mycophenolate, azathioprine, leflunomide, cyclosporine, belimumab, tacrolimus, or any other immunosuppressive agent not included in 1b.-f. above, when the dose of that immunosuppressive agent has increased within 3 months before Visit 1 (Day 1). Concurrent treatment with any of

these medications is allowed as long as the doses have been stable for at least 3 months before Visit 1 (Day 1)

- h. Actively listed on an organ transplantation list or have received an organ transplant other than a corneal transplant
- 2. Significant diseases or conditions other than SLE that may influence response to the study product or safety, such as:
 - a. Active bacterial or viral infection requiring systemic antibiotic or anti-viral treatment within 14 days before Visit 1 (Day 1)
 - b. Acute or chronic hepatitis B or C infection
 - c. Human immunodeficiency infection
 - d. History of active tuberculosis or positive tuberculosis skin or blood test without: 1) completing a course of appropriate treatment; or 2) having received at least one month of appropriate treatment prior to Visit 1 (Day 1) and continuing to receive appropriate treatment during the study
 - e. No elective surgery should be planned from Visit 1 (Day 1) through Visit 6 (Day 113)
 - f. A history of cancer. Except basal cell carcinoma or in situ carcinoma of the cervix treated with apparent success with curative therapy greater than one year before Visit 1 (Day 1)
 - g. Significant heart disease as defined by:
 - i. Uncontrollable congestive heart failure, unstable angina, unstable atherosclerotic cardiovascular disease, significant arrhythmia requiring chronic therapy, pulmonary arterial hypertension with dyspnea, disability rated as New York heart Association Grade III or higher, severe systemic hypertension or severe peripheral vascular disease
 - ii. Marked baseline prolongation of QT/QTc interval (i.e. repeated demonstration of a QTc interval \geq 450 msec for males and \geq 470 msec for females)
 - iii. History of risk factors for torsade de pointes (e.g., heart failure, hypokalemia)
 - iv. Clinically significant confirmed abnormality, as determined by the site investigator or qualified designee, on 12-lead ECG at Screening
- 3. History of chronic pain requiring treatment with narcotic analgesia for more than 30 days total within 6 months (183 days) of baseline. This does not include self-limited pain associated with identifiable events such as surgery
- 4. Current evidence of alcohol abuse (defined as 4 or more drinks per day on at least 4 days of the week) or history of abuse of illegal and/or legally prescribed drugs such as barbiturates, benzodiazepines, amphetamines, cocaine, or opioids during the 1 year prior to Screening
- 5. Currently pregnant, breast-feeding, or lactating

- 6. Any investigational agent within 30 days or five therapeutic half-lives of that agent whichever is longer, before Visit 1 (Day 1)
- 7. Any of the following values for laboratory tests at Screening:
 - a. A positive pregnancy test (also at Visit 1 (Day 1))
 - b. A newly positive QuantiFERON® blood test for tuberculosis, without: 1) completing a course of appropriate treatment; or 2) having received at least one month of appropriate treatment prior to Visit 1 (Day 1) and continuing to receive appropriate treatment during the study. If the subject has a previous documented positive tuberculosis skin, then this testing does not need to be repeated. If the subject has a documented negative test result within the last year, testing does not need to be repeated, at the discretion of the site investigator
 - c. Hemoglobin < 8 g/dL
 - d. Neutrophils $< 1.0 \times 10^9/L$
 - e. Platelets $< 75 \times 10^9/L$
 - f. eGFR < 50 ml/min according to Cockcroft-Gault equation
 - g. AST, ALT, or alkaline phosphatase > 2.0 x upper limit of normal
- 8. Any other conditions that, in the opinion of the site investigator, are clinically significant and may put the subject at greater safety risk, influence response to study product, or interfere with study assessments. When in doubt, the site investigator or qualified designee should discuss the situation with the Protocol Chairs.

4.3 Co-enrollment Guidelines

Enrolled subjects are allowed to continue participation in observational research studies that do not dictate treatment. Co-enrollment in another research study that dictates treatment in any way is not allowed from Screening through Visit 6 (Day 113).

4.4 Strategies for Recruitment and Retention

The target enrollment is 100 eligible subjects. Most subjects will be recruited from specialized academic outpatient SLE clinics run by the site investigators or at which the site investigators participate. A need to advertise for subjects outside the sites is not anticipated, although it is acceptable. If it becomes necessary to advertise, DAIT/NIAID will review and approve such advertisements to make sure they meet FDA requirements. Children, pregnant females, prisoners and other vulnerable populations will not be recruited. The clinical trial will be listed on clinicaltrials.gov and possibly other relevant websites to make information about this trial easily accessible on the internet.

To encourage retention in the study, every effort will be made to be respectful of the subject's time. The total time required from the subject will vary with the visit and the efficiency of each site and is expected to be 11-15 hours across all visits plus travel time. Absent any safety reason to withdraw from the study, subjects will be encouraged to stay in

the study at each visit by study personnel and reminded of the date and time of their next visit.

5 TREATMENT OF SUBJECTS

5.1 Description of Study Product

5.1.1 **Product Description**

Active Product: JBT-101 is (6aR, 10aR)-3-(1,1-dimethylheptyl)- Δ8-tetrahydro-cannabinol-9-carboxylic acid (see Figure 2), also known as Lenabasum, anabasum, resunab, ajulemic acid, CT-3, IP751 and CPL7075. It is a dimethylheptyl structural analogue of tetrahydrocannabinol-11-oic acid, designed and selected on the basis of cannabinoid structure-activity features associated with limited penetration of the blood-brain barrier, to reduce unwanted psychoactivity. JBT-101 has preferential binding to CB2 versus CB1 and exhibits preferential cellular activation through CB2 (Tepper et al., 2014). Detailed study product information can be found in the IB for JBT-101. The structure of JBT-101 is shown in Figure 2.

Figure 2. Structure of JBT-101

со ₂ н 	Molecular Formula:	$C_{25}H_{36}O_4$
* 0 он	Molecular Weight:	400.55
	CAS Number:	137945-48-3
H ⁺ H ₃ C 6 0 3 C(CH,)(CH,)(CH,)(CH)	Appearance:	White to tan powder
H ₃ C ⁵ ⁴		

JBT-101 is manufactured by Corbus Pharmaceuticals Holdings, Inc.

Comparator Product: Placebo is microcrystalline cellulose (no active ingredient), formulated to have an appearance and weight similar to JBT-101.

5.1.2 **Packaging and Labeling of Study Product**

JBT-101 5 mg and 20 mg and placebo are powder-in-capsule preparations packaged in identical no. 2 gelatin capsules. JBT-101 and placebo will be packaged in coded bottles of 35 capsules each that will be labeled in accordance with regulatory requirements. The bottles will be made of high density polyethylene with polypropylene child-resistant caps and an induction seal. Each bottle will contain a canister that absorbs oxygen.

Study product will be supplied in kits of two bottles per kit. Each bottle will be numbered to match the kit. Each kit will contain a 28-day supply of study product plus packaged overage

that is enough for another seven days of treatment, in case the next visit is delayed. In each kit, one bottle will be labeled for the morning dose and the other bottle will be labeled for evening dose, with written directions for morning or evening dosing and with visual clues about the time of dosing. Different kits will be manufactured to meet the needs of the study and will contain one of the following:

- Cohort 1 Kit: One bottle of JBT-101 5 mg for a.m. dose and one bottle of 5 mg for p.m. dose
- Cohort 2 Kit: One bottle of JBT-101 20 mg for a.m. dose and one bottle of placebo for p.m. dose
- Cohort 3 Kit: One bottle of JBT-101 20 mg for a.m. dose and one bottle of JBT-101 20 mg for p.m. dose
- Cohort 4 Kit: One bottle of placebo for a.m. dose and one bottle of placebo for p.m. dose

The bottles will be indistinguishable from each other in appearance, and the kits will be indistinguishable from each other in appearance.

JBT-101 will be dispensed to study subjects in the original packaging with a label clearly indicating that the contents are for investigational purposes only. The label will include conditions for storage, a unique drug ID, and other pertinent information such as Sponsor and caution statement. Neither JBT-101 nor placebo should be used after the expiration date unless a written notification of an expiration date extension is provided by the manufacturer.

If the packaging is damaged, or if there is anything unusual about the appearance or attributes of the pills or bottles, it should not be used. The study drug in question should be quarantined at the study site and the problem immediately reported to DAIT/NIAID or their representative.

5.1.3 **Storage and Handling of Study Product**

DAIT, NIAID will provide the investigational product for the conduct of this protocol and will be responsible for the disposal of unused product.

The investigational product will be stored at the site pharmacy or in the site investigator's locked storage cabinet/safe. Study product will to be stored at room temperature away from temperature and humidity extremes. Storage conditions must be appropriate for small quantities of Controlled Drugs Act Schedule 1 substances. The study product that is returned by the subjects to the site also will be stored under conditions appropriate for small quantities of Controlled Drugs Act Schedule 1, until disposal.

The site pharmacist, site investigator or qualified designee is responsible for investigational product accountability, maintaining accurate logs of study product received, dispensed, returned or destroyed, and ensuring the appropriate amount of study drug is kept on site and that it is used for research purposes only. He/she will perform drug accountability procedures

such as checking drug shipments against the shipping contents form, maintaining a log of the amount of study drug provided to individual subjects, and reconciling used and unused drug supply by subjects and the study unit.

Upon completion of the study, any unused investigational product(s) at the study sites will be returned to the drug distributor, as requested by DAIT/NIAID.

5.2 Dosage Regimen

The JBT-101 doses selected for this study are 5 mg b.i.d., 20 mg q.d., and 20 mg b.i.d. for oral administration without regard for fed/fasted state. JBT-101 will be administered orally b.i.d. on Days 1-84, with at least 8 hours between doses. (See Section 3.1, *Description of Study Design*; Table 1.)

5.3 Administration of Study Product

JBT-101 will be self-administered orally b.i.d., with at least 8 hours between doses and without regard to fed state. See Section 3.1, *Description of Study Design*; Table 1 for morning and evening dosing for the 4 cohorts. The first dose of JBT-101 at Visit 1 (Day 1) will be taken in the clinic, and the subjects will be observed in the clinic for at least 30 minutes after this dose or longer, until, in the opinion of the investigator, vital signs and clinical symptoms are acceptable for the subject to leave the clinic. After this observation period, subjects must still be available for additional assessments 2.5 to 3.5 hours after administration of the study product.

JBT-101 should be taken in the following way:

- JBT-101 and placebo capsules should be swallowed whole, with liquid as helpful, and should not be broken, chewed or opened. Morning and evening doses should be at least 8 hours apart.
- If a dose of JBT-101 or placebo is missed, it should be taken as soon as possible on the same day, as long as the other dose that day can be timed to be at least 8 hours separate from the time of the missed dose. If it is missed for the entire day, it should not be made up.
- Doses can be taken without regard to fed state.

Subjects who take more than the prescribed dose of JBT-101 or placebo should be instructed to seek emergency medical care, if needed, and to contact the study staff as soon as possible.

5.4 Management Plan for Potential Risks

As of July 2017, no severe AEs have been found to be definitely related to JBT-101. As such, the plans detailed in the section are proposed as general precautions for potential risks.

Expected AEs related to JBT-101 are via CB receptors. As of July 2017, a number of the AEs associated with CB1/CB2 agonists have been reported in subjects exposed to JBT-101, such as fatigue, dizziness, decreased concentration, feeling "weird", lightheadedness,

asthenia, somnolence, nausea, vomiting, mild orthostatic hypotension, and dry mouth. Patients in the study will be monitored closely for all of these side effects as well as for potential toxicities including psychotropic, gastrointestinal and cardiovascular effects. They are scheduled to be seen frequently during the treatment period (on study Days 1, 15, 29, 57 and 85) and on day 113 for safety follow-up. The ARCI-M scale will be used to assess psychotropic effects of the drug. The Lupus Activity Patient Global Assessment, PROMIS-29 Short Form and PROMIS Item Bank v2.0 - Cognitive Function will be used to assess fatigue and quality of life. The IVRS e-diary for the NRS scale will be used to record pain on a daily basis. Disease activity will be evaluated using patient history, physical exams, hematologic, blood chemistries, urinalyses and serologies pertinent to the SLEDAI (C3, C4 and anti-dsDNA antibodies).

Prolongations of QTc interval to less than 500 msec total and up to 39 msec prolongation from pre-treatment baseline were observed in a previous Phase 1 study, and all of these prolongations were judged not clinically significant. They were only observed in some subjects ≥ 65 years of age exposed to JBT-101 at a total daily dose of up to 180 mg for seven days. For this reason, to ensure safety of subjects, the QT/QTc interval will be measured throughout the study, and maximum doses tested will not exceed 40 mg/day (given as 20 mg b.i.d.).

If a subject develops a grade 3 or higher NCI-CTCAE (version 4.0) adverse event that is deemed by the blinded site investigator to be possibly related, probably related, or related to study drug, the subject will be discontinued from treatment but will continue to be monitored at the scheduled follow-up visits unless consent is withdrawn.

There will be no dose modification in this study, other than temporary or permanent discontinuation of study drug and there is no rescue treatment.

5.4.1 **Prevention of Potential Risks to Study Product**

The Inclusion/Exclusion criteria have been designed to exclude subjects with significant other illnesses or conditions that would increase safety risks during the trial. Subjects with chronic pain requiring ongoing treatment with narcotic analgesia are also excluded. Subjects will additionally be reminded to call their study physician in the event that they develop any adverse event (whether or not they determine it to be related to the study) and may be evaluated for potential toxicity at an unscheduled visit.

5.4.2 Management of Potential Risks to Study Product

Severe symptoms related to the potential risks of JBT-101 may necessitate stopping study drug. Stopping study drug is not a reason for withdrawal from the study, but a subject may be withdrawn at the discretion of the PI if deemed it is in the subject's best interest.

For subjects who experience potential CB1/CB2 mediated AEs (fatigue, dizziness, decreased concentration, feeling "weird", lightheadedness, asthenia, somnolence, GI disturbances such as nausea or vomiting, or dry mouth), treatment for symptoms should be prescribed as needed, and study treatment may be withheld at discretion of PI.

5.5 Concurrent Medications and Therapy

The intent is that each subject is maintained on all his/her medications for SLE from Screening through Visit 6 (Day 113), unless the site investigator or other treating physicians judge that a change in therapy is needed to provide best medical care for the subject. Information about the concomitant medications and treatments will be collected at each Visit. All concomitant medications given to the subject during the study will be recorded on the eCRF.

Concomitant therapies taken for the long term treatment of pre-existing conditions other than SLE may be continued during the study provided they are in accordance with the exclusion criteria. It is preferred that these medications be stabilized before entry and continued wherever practical without variation of dose or regimen during the study.

During the study, concomitant medications and new medications should be administered at the discretion of the site investigator or treating physician in order to provide the subject with the best possible medical care. Because of the unavailability of toxicology data or clinical experience of JBT-101 in combination with many therapeutic agents, it is recommended that changes in ongoing treatments or introduction of new therapies are kept to a minimum. The benefit: risk to the subject should be carefully assessed and consideration given to the timing of any necessary introductions of new medications.

Permitted concomitant medications for SLE during the study include stable doses, including stable doses of as needed (prn) medication, of any of the following:

- Anti-malarial medications
- Systemic corticosteroids $\leq 10 \text{ mg q.d. or} \leq 20 \text{ mg every other day oral prednisone or equivalent corticosteroid}$
- Methotrexate, mycophenolate, azathioprine, leflunomide, belimumab, cyclosporine, or tacrolimus
- Topical therapies, such as topical corticosteroids, antibiotics, anti-viral agents, artificial tears, ophthalmic ointments
- NSAIDS, dosing must be held within 12 hours of certain study Visits (see Table 2 below)
- Non-narcotic and narcotic analgesic, dosing of must be held within 6 or 12 hours, based on half-life of the analgesic, of certain study Visits (see Table 2). Narcotic analgesics are permitted only for prn use for acute events not related to SLE disease activity
- Other medications not specifically included in this list of allowed concomitant medications for SLE are allowable, based on the judgment of the investigator and provided they are not included in the list of disallowed medications (Table 2)

5.6 **Prohibited Medications**

A list of disallowed medications is provided in Table 2.

Drug Class	Requirements	
Analgesics with half-life < 6 hours	Prohibited for 6 hours prior to study	
	assessments at Visits 1, 3, 4, 5, and 6	
NSAIDS and analgesics with half-life ≥ 6	Prohibited for 12 hours prior to study	
hours	assessments at Visits 1, 3, 4, 5, and 6	
Systemic corticosteroids > 10 mg per day or > 20 mg every other day oral prednisone or equivalent corticosteroid or increase in dose of systemic corticosteroid	To accommodate the occasional use of extra corticosteroids by patients for reasons not associated with SLE flares, increases of up to 20 mg/day that are decreased back to the baseline dose within 7 days are permitted, but not on more than 2 occasions during the study. These short increases in dose may not be accompanied by a documented SLE disease flare. However, use is prohibited for 14 days prior to study visits for Screening.	
Intraarticular, intravenous, or	Prohibited for 14 days prior to study visits for	
intramuscular systemic corticosteroids	Screening and during the study	
Any cannabinoid, cannabinoid-mimic	Prohibited from Screening through Visit 6 (Day	
(except JBT-101), or illegal substance of abuse	113)	
Cyclophosphamide or anti-TNFα biologic	Prohibited for 3 months before Visit 1 (Day 1)	
agents	and during the study	
Rituximab, ocrelizumab, anti-CD22	Prohibited for 6 months before Visit 1 (Day 1)	
monoclonal antibody	and during the study	
Other investigational agents	Prohibited for 30 days or 5 half-lives before Visit 1 (Day 1), whichever is longer and during the study	

Page 50 of 125

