2.2 Secondary Objective(s)

The secondary objectives are to:

- 1. Evaluate efficacy of JBT-101 in active musculoskeletal disease in SLE
- 2. Evaluate efficacy of JBT-101 in overall disease activity in SLE
- 3. Evaluate efficacy of JBT-101 in patient-reported outcomes in SLE
- 4. Evaluate the safety and tolerability of JBT-101 in subjects with SLE
- 5. Evaluate the effects of JBT-101 on biomarkers of inflammation in SLE
- 6. Evaluate the effects of JBT-101 on bioactive lipids in SLE
- 7. Evaluate JBT-101 plasma concentrations and metabolites in SLE

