For therapeutic stability, subjects should remain on their current treatment regimen for SLE from Screening through Visit 6 (Day 113), unless the site investigator or other treating physician judges that a change in therapy is needed to provide best medical care for the subject. If a subject experiences an increase in disease activity of SLE during participation in the study, he/she should be treated with standard of care for that increase in activity. If medically appropriate, some drugs that would interfere with evaluation of efficacy should be withheld for specified durations prior to certain study visits. See Section 5.6, *Prohibited Medications* for details.

Concomitant therapies taken for the long term treatment of pre-existing conditions other than SLE may be continued during the study provided they are in accordance with the exclusion criteria (Section 4.2, *Exclusion Criteria*). It is preferred that these medications be stabilized before entry and continued wherever practical without variation of dose or regimen during the study. Concomitant medications and new medications should be administered at the discretion of the site investigator or treating physician in order to provide the subject with the best possible medical care. Because of the unavailability of toxicology data or clinical experience of JBT-101 in combination with many therapeutic agents, it is recommended that changes in ongoing treatments or introduction of new therapies are kept to a minimum. The benefit: risk to the subject should be carefully assessed and consideration given to the timing of any necessary introductions of new medications.

Because this is an early study and no efficacy has been demonstrated in SLE, there are no plans to provide the subject with open-label JBT-101 after the study period. If they so choose, subjects may continue to be seen in the site investigator's clinical practice.

About 150 individuals will be screened to identify 100 eligible subjects, for a screen failure rate of about 33%. The number of subjects enrolled may be expanded by up to nine additional subjects, if these additional eligible subjects have signed the Informed Consent Form and are actively engaged in the screening process at the time 100 subjects have been randomized into the study.

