3.2.4 Mechanistic Endpoints

- 1. Trends in C-reactive protein levels in the blood over the duration of the treatment period (i.e. Visit 1 (Day 1) through Visit 5 (Day 85)) will be evaluated longitudinally
- 2. Persistence of trends in C-reactive protein levels after stopping treatment will be evaluated at Visit 6 (Day 113)
- 3. Trends in pro-inflammatory cytokine levels over the duration of the treatment period (i.e. Visits 1 (Day 1), 3 (Day 29) and 5(Day 85)) will be evaluated longitudinally using multiple indices:
 - Pro-inflammatory cytokines in serum
 - i. IFN α , IFN γ , IL-6, TNF α , and IL-1 β
 - ii. Expression of other cytokine will be explored
 - Pro-inflammatory cytokines in whole blood with and without in vitro TLR stimulation
 - i. IFN α , IFN γ , IL-6, TNF α , and IL-1 β in supernatant of stimulated and unstimulated whole blood cells
 - Type 1 IFN gene signature in whole blood mRNA

- 4. Persistence of trends in biomarkers of inflammation after stopping treatment will be evaluated at Visit 6 (Day 113)
- 5. Changes in bioactive lipids in plasma from Visit 1 (Day 1) (pre and post dose) to Visit 2 (Day 15) will be evaluated longitudinally using multiple indices:
 - Specialized Pro-resolving lipid Mediators (SPMs), including lipoxin A4
 - Anti-inflammatory eicosanoids
 - Pro-inflammatory eicosanoids
- 6. Changes in plasma concentrations of JBT-101 and its metabolites from Visit 1 (Day 1) (pre and post dose) to Visit 2 (Day 15)

3.2.5 **Exploratory Endpoints**

1. Changes in Fibromyalgia Symptom Scale score, from Visit 1 (Day 1) to Visits 5 (Day 85) and 6 (Day 113)

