6.3.2 Metabolipidomic Profile

Metabolipidomic profiles will be assessed in plasma at Visit 1 (Day 1) and Visit 2 (Day 15). At Visit 1 (Day 1), metabolipidomic profiles will be assessed before and 2.5 to 3.5 hours after study product is administered. The metabolipidomic profiles will include measurement of certain SPMs, anti-inflammatory eicosanoids, and pro-inflammatory eicosanoids. As possible, the blood samples for metabolipidomic profile testing should be collected at least 2 hours after the last solid meal.

6.3.3 **JBT-101 Plasma Concentrations and Metabolites**

Plasma concentrations of JBT-101 and its metabolites will be measured at Visit 1 (Day 1) and Visit 2 (Day 15). At Visit 1 (Day 1), plasma levels of JBT-101 and metabolites will be measured before and 2.5 to 3.5 hours after study product is administered.

JBT-101 plasma concentrations and metabolites will be measured using validated assays [101]. Collection at 3 hours after dosing should provide concentrations near peak plasma concentrations and first pass metabolites.

6.3.4 **Optional Unspecified Future Studies**

If the subject provides written informed consent, extra serum and leftover specimens derived from blood samples, including serum, plasma, mRNA, whole blood cells, and whole blood cells culture supernatants, will be stored for future unspecified studies related to JBT-101, the immune system, or SLE.

In addition, if appropriate consents are given, peripheral blood mononuclear cell (PBMC) samples for future, unspecified, IRB approved studies related to JBT-101, the immune system, or SLE will be collected at Visit 1 (Day 1) and follow-up visits per Table 3, *Schedule of Events*.

6.3.5 **Blood Draw Prioritization**

The volume of blood to be drawn at a given visit is limited under the following situations:

- Should the subject have been experiencing severe anemia (hemoglobin < 8g/dL) or have poor venous access, the blood draw limit is 30 mL.
- Should the subject have been experiencing moderate-severe anemia (hemoglobin 8-9 g/dL), the blood draw limit is 50 mL.

• In any patient whose clinical condition might be adversely affected by removal of the volumes required for this protocol, for example, patients with significant anemia (as noted above) or compromised cardiac output, investigators should consider further limiting the volume of blood withdrawn for research purposes.

The priority of samples to collect is as follows:

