6.4.1.1 Evaluation of Eligibility and Randomization

The subject's average of 7-day maximum daily pain NRS score will be computed by the IVRS and reported to site personnel.

If the average is \geq 4, and the subject meets other eligibility criteria for enrollment, then proceed as follows:

- Instruct the subject to continue to record maximum daily pain NRS score using the IVRS. Randomization will not be allowed, if compliance with reporting falls below 67% during the Screening period.
- Schedule Visit 1 (Day 1) (within 42 days of 1st Screening assessment)
 - Randomizations must occur at least 7 days prior to Visit 1 to ensure that drug will be available on site for Visit 1.
 - Instruct eligible subjects to hold short-acting analgesics for 6 hours and NSAIDs and long-acting analgesics for 12 hours prior to Visit 1 (Day 1).
- Randomize the subject (ensure sufficient time for shipment of study drug prior to the scheduled Visit 1 (Day 1))

If the subject is not eligible, inform the subject and let them know IVRS will no longer accept daily entries.

6.4.2 **Treatment Period**

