 - Remind subject to refrain from taking morning dose before Visit 2. Subjects with visits after 2 PM will be instructed to take their morning dose. This is being done to measure trough plasma concentration of JBT-101 at specified visits.

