6.4.2.2 Visit 2 (Day 15 ± 3 days)

The following procedures will be performed:

- Record concomitant medications
- Vital signs: weight, blood pressure, pulse, respiratory rate, and temperature
- AE monitoring
- Blood tests
 - Hematology: CBC with differential cell count and platelets
 - Chemistry: Complete metabolic panel, including electrolytes, renal function, and liver function tests
- Blood draws for mechanistic studies
 - Plasma: metabolipidomic profile, and JBT-101 plasma concentrations and metabolites; sampled ≥ 2 hours after last solid meal, if possible
 - PBMC: future use (if subject provided written consent)
- Count and record number of capsules the subject has remaining
- Instruct subjects to hold short-acting analgesics for 6 hours and NSAIDs and longacting analgesics for 12 hours prior to the assessments at Visit 3 (Day 29) and remind them to bring the bottles of study drug with them to their next visit.

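### NSAIDs are held for 12 h before Visit 1 but not before Visit 2, so the within-arm Day 1 to Day 15 prostaglandin change can include resumed NSAID intake (minor)

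*Protocol*

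**What the plan says.** **The hold.** NSAIDs are permitted at stable doses, as-needed use included (Section 5.5). Table 2 in Section 5.6 prohibits them for 12 hours before "assessments at Visits 1, 3, 4, 5, and 6". Section 3.1 gives the reason: "some drugs that would interfere with evaluation of efficacy should be withheld for specified durations prior to certain study visits".

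**The visit instructions agree with Table 2.** Section 6.4.1.1 has sites tell subjects about the hold before Visit 1. The Visit 1 reminders in Section 6.4.2.1 look ahead to Visit 2 but cover only the drug bottles and the study-drug dose: "Remind subject to refrain from taking morning dose before Visit 2". The hold instruction given at Visit 2 (Section 6.4.2.2) concerns the following visit: "analgesics for 12 hours prior to the assessments at Visit 3 (Day 29").

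**The lipid draws.** Section 6.3.2 says "Metabolipidomic profiles will be assessed in plasma at Visit 1 (Day 1) and Visit 2 (Day 15"). At Visit 1 there is a draw before and a draw 2.5 to 3.5 hours after dosing. Table 3 marks the lipid sample at no other visit. Mechanistic endpoint 5 (Section 3.2.4) reads "Changes in bioactive lipids in plasma from Visit 1 (Day 1) (pre and post dose) to Visit 2 (Day 15) will be evaluated longitudinally", and it serves secondary objective 6: "Evaluate the effects of JBT-101 on bioactive lipids in SLE".

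**What is recorded.** Section 6.1.2 lists the drug, dose, frequency, route, dates and indication. The time of last intake is not on that list.

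**The concern.** A change score is easiest to read when both samples are taken under the same conditions. Here a drug class expected to act on part of the panel is withheld before the first sample and unrestricted before the second. Background Sections 1.2.1 and 1.2.3 name PGE2 among the pro-inflammatory eicosanoids, and PGD2 and PGJ2 among the anti-inflammatory ones that the drug is said to raise. Resumed NSAID intake by Day 15 could lower PGE2, which would resemble the drug effect, and could lower PGD2 and PGJ2, which would mask it.

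The protocol already standardises these draws in two other ways: time since the last solid meal, and the withheld morning study dose at Visit 2. NSAID timing is the gap. At stake are the reading of the within-arm change and the precision of the placebo contrast for one mechanistic endpoint.

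**Working it through.** **1. Schedules side by side.** There is no stated figure to reproduce.

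- Visits with an NSAID hold (Table 2 and the visit instructions): {1, 3, 4, 5, 6}
- Visits with lipid draws (Section 6.3.2, Table 3): {1, 2}
- Overlap: {1}

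Baseline is sampled under the hold and the Day 15 follow-up is not. Adding Visit 2 to the hold makes the overlap {1, 2}.

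**2. Size: illustration only.** The documents give no NSAID prevalence, suppression, recovery after 12 hours or assay variability. Every input here is assumed:

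- u = fall in a user's prostaglandin level from a held to an unrestricted sample, 0 to 80% (0 if a 12-hour hold restores nothing)
- q = share of an arm taking an NSAID within 12 hours before Visit 2, 10 to 60%
- s = other SD of the change, 30 to 100% of the level

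| Quantity | Formula | Result |
|---|---|---|
| Within-arm fall | q × u | 0.1 × 0 = 0 to 0.6 × 0.8 = 0.48 |
| Expected difference from placebo, equal q | (q − q) × u | 0 |
| Difference if q differs by 10 points | 0.1 × u | 0 to 0.08 |
| Added relative variance, middle inputs (q = 0.3, u = 0.4, s = 0.6) | q(1 − q)u²/s² | 0.21 × 0.16/0.36 = 0.093 |
| Added relative variance, extreme inputs (q = 0.5, u = 0.8, s = 0.3) | q(1 − q)u²/s² | 0.25 × 0.64/0.09 = 1.78 |

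The upper ends reflect the chosen inputs and are not evidence about this trial.

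**3. What an added Visit 2 hold would do to the primary endpoint.** The Day 14 and 15 pain scores enter the primary model, since Section 8.3.2.1 excludes only scores after discontinuation or on narcotic days. With complete data on Days 1 to 84, fit a quadratic in time and take the contrast of the Day 84 mean minus the Day 1 mean. The quadratic term cancels because Days 1 and 84 are equidistant from 42.5. The weight of day t is then 83 × (t − 42.5)/Σ(t − 42.5)², where the sum is 84 × (84² − 1)/12 = 49,385. The weight is the same under generalised least squares with the pooled covariance in Table 5.

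- Day 14: 83 × (−28.5)/49,385 = −0.048
- Day 15: 83 × (−27.5)/49,385 = −0.046
- Visit 2 window, Days 12 to 18: −0.051 to −0.041
- Day 28, the day before the existing Visit 3 hold: −0.024

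With an assumed 60% of users and a 2-point rise on both days, an arm moves by 0.6 × 2 × (−0.0479 − 0.0462) = −0.11 points. This is the same in every arm, so the expected shift against placebo is 0.

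**The case against.** The strongest reply is that nothing here is misstated. The hold was written for efficacy assessments, Visit 2 has none, and Table 2 agrees with the visit instructions. That stands: this is a design gap and not a contradiction, and a reader who infers an internal inconsistency goes too far.

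A reader might also infer that the lipid comparison with placebo is biased. The documents do not support that. One rule applies to all arms, and bias would need as-needed NSAID use to diverge by arm by Day 15. Inclusion criterion 8 and the stable-dose rule in Section 5.5 work against that.

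Nor is the acute comparison at Visit 1 mismatched. Table 2 ties the hold to the assessments at Visit 1, and the post-dose draw is one of that visit's procedures, so on a plain reading both samples are covered.

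Two further points stand. The endpoint names no prostaglandin; they come from background text and the full panel is not listed. And Section 1.6.4 makes the mechanistic work depend on whether the clinical results justify it.

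The reply that the separate mechanistic analysis plan (Section 8.3.5) can deal with this holds only in part. NSAID users and scheduled regimens can be identified from the medication record. As-needed intake in the hours before a draw cannot be recovered later if it was never recorded, and the Section 6.1.2 list does not include it. The eCRF itself is not at hand.

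**Conclusion.** The point holds as a minor one. The two visits that define the lipid change differ in NSAID restriction. Assuming NSAIDs lower prostaglandins, the within-arm Day 1 to Day 15 prostaglandin change can mix any drug effect with resumed NSAID intake. The placebo contrast carries avoidable noise and no expected bias unless as-needed use differs by arm.

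The size cannot be derived from the documents. It may be zero, and the illustrative upper values rest wholly on assumed inputs. The scope is prostaglandins only: no effect on SPM levels is claimed, and the primary endpoint, power, safety and clinical secondary endpoints are not affected by the mismatch. It would be wrong to conclude that secondary objective 6 cannot be met, because the randomised comparison and the Visit 1 pre- to post-dose comparison both remain usable.

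**What to change.** Record the time of last NSAID intake at each lipid draw (Visit 1 pre-dose, Visit 1 post-dose, Visit 2), for adjustment or a sensitivity analysis. This costs one eCRF time field and asks nothing more of pain control.

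Optionally, add Visit 2 to the 12-hour hold, with one line in the Visit 1 reminders, which already carry an instruction for Visit 2. Table 2 puts NSAIDs in the same row as long-acting analgesics, so word the Visit 2 hold for NSAIDs only. The cost is a sixth 12-hour NSAID hold in subjects with at least moderate pain. It may slightly raise pain scores around Days 14-15, with the small effect on the primary model worked out above, equal across arms in expectation. If that burden is unwelcome, the time field alone is enough to make the data interpretable.
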